8.3 Reporting of Serious Adverse Events and Unanticipated Problems

When an adverse event has been identified, the study team will take appropriate action necessary to protect the study participant and then complete the Study Adverse Event Worksheet and log. The sponsor-investigator will evaluate the event and determine the necessary follow-up and reporting required.

8.3.1 Sponsor-Investigator reporting: notifying the Mayo IRB

The sponsor-investigator will report to the Mayo IRB any UPIRTSOs and Non-UPIRTSOs according to the Mayo IRB Policy and Procedures.

Information collected on the adverse event worksheet (and entered in the research database):

- Subject's name:
- Medical record number:
- Disease/histology (if applicable):
- The date the adverse event occurred:
- Description of the adverse event:
- Relationship of the adverse event to the research (drug, procedure, or intervention):
- If the adverse event was expected:
- The severity of the adverse event: (use a table to define severity scale 1-5)
- If any intervention was necessary:
- Resolution: (was the incident resolved spontaneously, or after discontinuing treatment)
- Date of Resolution:

The sponsor-investigator will review all adverse event reports to determine if specific reports need to be made to the IRB and FDA. The sponsor-investigator will sign and date the adverse event report when it is reviewed. For this protocol, only directly related SAEs/UPIRTSOs will be reported to the IRB.

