8.1 Definitions

Unanticipated Problems Involving Risk to Subjects or Others (UPIRTSO)

Any unanticipated problem or adverse event that meets the following three criteria:

- Serious: Serious problems or events that results in significant harm, (which may be physical, psychological, financial, social, economic, or legal) or increased risk for the subject or others (including individuals who are not research subjects). These include: (1) death; (2) life threatening adverse experience; (3) hospitalization - inpatient, new, or prolonged; (4) disability/incapacity - persistent or significant; (5) birth defect/anomaly; (6) breach of confidentiality and (7) other problems, events, or new information (i.e. publications, DSMB reports, interim findings, product labeling change) that in the opinion of the local investigator may adversely affect the rights, safety, or welfare of the subjects or others, or substantially compromise the research data, **AND**
- Unanticipated: (i.e. unexpected) problems or events are those that are not already described as potential risks in the protocol, consent document, not listed in the Investigator's Brochure, or not part of an underlying disease. A problem or event is

"unanticipated" when it was unforeseeable at the time of its occurrence. A problem or event is "unanticipated" when it occurs at an increased frequency or at an increased severity than expected, AND

- Related: A problem or event is "related" if it is possibly related to the research procedures.

Adverse Event

An adverse event is any untoward medical occurrence in a clinical study subject administered a medicinal (investigational or non-investigational) product. An adverse event does not necessarily have a causal relationship with the treatment. An adverse event can therefore be any unfavorable and unintended sign (including an abnormal finding), symptom, or disease temporally associated with the use of a medicinal (investigational or non- investigational) product, whether or not related to that medicinal (investigational or non-investigational) product. (Definition per International Conference on Harmonisation [ICH])

This includes any occurrence that is new in onset or aggravated in severity or frequency from the baseline condition, or abnormal results of diagnostic procedures, including laboratory test abnormalities.

Serious Adverse Event

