8.2 Recording of Adverse Events

At each contact with the subject, the study team must seek information on adverse events by specific questioning and, as appropriate, by examination. Information on all adverse events should be recorded immediately in the source document, and also in the appropriate adverse event section of the case report form (CRF). All clearly related signs, symptoms, and abnormal diagnostic, laboratory or procedure results should be recorded in the source document.

All adverse events occurring during the study period must be recorded. The clinical course of each event should be followed until resolution, stabilization, or until it has been ultimately determined that the study treatment or participation is not the probable cause. Serious adverse events that are still ongoing at the end of the study period must be followed up, to determine the final outcome. Any serious adverse event that occurs after the study period and is considered to be at least possibly related to the study treatment or study participation should be recorded and reported immediately.

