8.3.2 Sponsor-Investigator reporting: Notifying the FDA

The sponsor-investigator will report all serious, unanticipated and possibly drug related events to the FDA utilizing the Voluntary Reporting Form 3500. See FDA information on Reporting for NON IND Events:

<http://www.fda.gov/Safety/MedWatch/HowToReport/ucm085568.htm>

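### Section 8.3.1 limits IRB reports to directly related events, contradicting its own opening sentence and the possibly-related test in the Section 8.1 UPIRTSO definition

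*Combined protocol and SAP*

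**What the plan says.** Section 8.3.1 gives two rules for what reaches the IRB. It opens: "The sponsor-investigator will report to the Mayo IRB any UPIRTSOs and Non-UPIRTSOs according to the Mayo IRB Policy and Procedures". After listing the contents of the adverse event worksheet, it closes by saying that, for this protocol, "only directly related SAEs/UPIRTSOs will be reported to the IRB".

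Section 8.1 defines a UPIRTSO as "Any unanticipated problem or adverse event that meets the following three criteria": serious, unanticipated and related. For the third criterion, a problem or event is related "if it is possibly related to the research procedures".

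Under Section 8.3.2 the sponsor-investigator "will report all serious, unanticipated and possibly drug related events to the FDA". Section 8.2 says that a serious event arising after the study period and "considered to be at least possibly related to the study treatment or study participation should be recorded and reported immediately", without naming the recipient. Section 8.3.3.8.1 sends all SAEs after exposure to the manufacturer, with no relatedness condition.

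**The concern.** Safety is the primary objective (Section 2), and the IRB is one of the bodies that must judge whether the risk remains acceptable. The closing sentence of 8.3.1 decides which events it sees, and it uses a relatedness standard that appears nowhere else in the protocol.

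The choice of word matters in this design. There are 12 patients and no control group, and Section 1.4 says that most untreated patients progress to end-stage renal disease. Section 4.2 allows entry on MMF, cyclosporine, tacrolimus or azathioprine, which stop when daratumumab starts. With those competing explanations, an unexpected serious event in one patient may well be classed as possibly related, and direct causation is hard to establish from a single case. Two staff members applying Section 8.3.1 in good faith could reach opposite decisions about such an event.

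**Working it through.** No arithmetic applies. The check sets the relatedness conditions side by side and then runs four kinds of event through them.

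| Place | Recipient or use | Relatedness condition |
|---|---|---|
| 8.1, UPIRTSO definition | Defines the reportable problem | Possibly related to research procedures |
| 8.2, events after the study period | Recipient not named | At least possibly related to treatment or participation |
| 8.3.1, opening sentence | IRB | None beyond the UPIRTSO definition; IRB policy applies |
| 8.3.1, closing sentence | IRB | Directly related (undefined) |
| 8.3.2 | FDA | Possibly drug related |
| 8.3.3.8.1 | Manufacturer | None |

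On relatedness alone, the closing sentence of 8.3.1 is the outlier. Its opening words make it specific to this protocol and exclusive, so a reader would naturally take it as the operative rule.

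1. **Serious, unanticipated, directly related.** It meets the UPIRTSO definition, goes to the FDA, and goes to the IRB under both sentences. There is no conflict.
2. **Serious, unanticipated, possibly but not directly related to the drug.** It goes to the FDA under 8.3.2. It meets the 8.1 definition if the study drug counts as part of the research procedures. The worksheet in 8.3.1 supports that reading, because it lists the drug among the things meant by the research when relationship is recorded. The opening sentence of 8.3.1 sends the event to the IRB; the closing sentence withholds it.
3. **Serious, expected, possibly related**, such as pneumonia or a cytopenia at the expected frequency and severity. Section 1.4 already lists these as risks, so the event fails the unanticipated criterion in 8.1. It is not a UPIRTSO, and 8.3.2 does not send it to the FDA. Whether the opening sentence sends it to the IRB depends on IRB policy, which is not in the documents.
4. **Serious decline in kidney function from the disease itself.** Section 8.1 excludes events that are part of the underlying disease from being unanticipated, so the result is the same as in case 3.

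Only case 2 produces an event that meets the protocol's own definition, goes to the FDA and is kept from the IRB. Cases 3 and 4 can move into case 2 only if the event is more frequent or more severe than expected, because 8.1 then treats it as unanticipated.

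**The case against.** The strongest reply is that the closing sentence need not override anything. The opening sentence invokes IRB policy, which may govern in practice. Grammatically, *directly related* could also qualify only the SAEs, leaving every UPIRTSO reportable. This stands in part: the policy cannot be seen, so an actual loss of reports cannot be shown. It does not remove the conflict. If the policy governs, the closing sentence is redundant or in conflict with it. If the qualifier covers only SAEs, the text should say so.

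A second reply is that other oversight exists. The DSMB is not affiliated with the study, its chair is told of SAEs within 48 hours of their being reported (Section 7.2), and it receives all adverse event reports (Section 8.5.1). The manufacturer receives all SAEs, and the stopping rule in 8.4 has no relatedness condition. This stands and limits the harm. It does not replace the IRB reports to which 8.3.1 commits.

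A reader might go further and infer that the IRB would miss most of the serious events it needs, because these patients are prone to infection and kidney decline. The documents do not support that. At expected frequency and severity those events generally fail the unanticipated criterion, so they are neither UPIRTSOs nor reportable to the FDA under 8.3.2, whichever relatedness word is used. Nor can the gap be expressed as a share of the 12 patients, since any such figure would rest on a supposed number of events.

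**Conclusion.** Section 8.3.1 contradicts itself, and its closing sentence contradicts the UPIRTSO definition in Section 8.1. Followed literally, it withholds from the IRB those serious, unanticipated events judged possibly but not directly related. Where the suspected cause is the drug, the same events go to the FDA.

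The conclusion rests on two assumptions: that the closing sentence is read as applying to both SAEs and UPIRTSOs, and that the study drug counts as part of the research procedures. The effect is on safety oversight only. Section 8.2 requires all adverse events to be recorded, so the primary endpoint counts and their analysis do not change. The number of events affected cannot be estimated from the documents. The correction should be made because it concerns patient protection and is cheap, but it does not threaten the trial's results.

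**What to change.** Replace the closing sentence of Section 8.3.1 with a rule tied to the definition. For example: all events meeting the Section 8.1 definition of a UPIRTSO (serious, unanticipated, and at least possibly related to the research, including the study drug) will be reported to the IRB; other SAEs will be reported as IRB policy requires. Check the wording against that policy before it is adopted.

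Simply changing *directly* to *possibly* would be a poorer repair. Because the sentence covers SAEs as well as UPIRTSOs, it would also send expected, possibly related SAEs to the IRB, whether or not the policy asks for them. It would also leave open whether the drug is included, since 8.1 speaks of research procedures and 8.3.2 of the drug.

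The cost is one sentence and possibly a few more IRB reports. Treatment, endpoints, sample size and analysis are untouched.

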8.3.2 Sponsor-Investigator reporting: Notifying the FDA

The sponsor-investigator will report all serious, unanticipated and possibly drug related events to the FDA utilizing the Voluntary Reporting Form 3500. See FDA information on Reporting for NON IND Events:

<http://www.fda.gov/Safety/MedWatch/HowToReport/ucm085568.htm>

8.3.3 Sponsor-Investigator reporting: Notifying the Manufacturer

Interventional IIS Janssen Scientific Affairs Requirements for Safety Data Collection and Reporting

8.3.3.1 Overview

As the sponsor of the Study, Mayo Clinic and PRINCIPAL INVESTIGATOR shall be solely responsible for complying, within the required timelines, any safety reporting obligation to competent Health Authorities, IRB/ECs and any participating (co or sub) investigators, as defined in applicable laws and regulations. For the purposes of this section, safety data includes adverse events, product quality complaints (PQCs), and special situations including pregnancies.

The Mayo Clinic and PRINCIPAL INVESTIGATOR will provide safety information to Janssen Scientific Affairs, LLC on adverse events, special situations including pregnancies and product quality complaints as defined within this section.

8.3.3.2 Management of Safety Data

This Study has been designated as an interventional study. As such, all adverse events for Janssen Medicinal Products regardless of causality and special situations excluding those from subjects not exposed to a Janssen Medicinal Product and product quality complaints with or without an adverse event as described in this Exhibit will be reported from the time a subject has signed and dated an Informed Consent Form (ICF) until 30 days after completion of the subject's last study-related procedure (which may include contact for follow-up safety). Serious adverse events will be reported for 30 days after the last dose of study drug.

For the purposes of this study, the Janssen medicinal product is: DARZALEX® (daratumumab)

8.3.3.3 Definitions

Adverse Event (AE)

See Adverse Event Definition in Section 8.1 above

Adverse Events of Special Interest

Adverse events of special interest are events that Janssen Scientific Affairs, LLC is actively monitoring as a result of a previously identified signal (even if non-serious). These adverse events are:

- Infusion reactions: \geq grade 3
- Infections: \geq grade 4
- Cytopenias: \geq grade 4
- Tumor lysis syndrome
- Other malignancies
- Intravascular hemolysis – all grades

Any Adverse Event of Special Interest that is to be reported to the COMPANY should be recorded on a Serious Adverse Event Report Form and be reported to the COMPANY within 24 hours of knowledge of the event.

Individual Case Safety Report (ICSR)

A valid ICSR must contain the four minimum criteria required to meet regulatory reporting requirements.

- an identifiable subject (but not disclosing personal information such as the subject's name, initials or address)
- an identifiable reporter (investigational site)
- a Janssen medicinal product
- an adverse event, outcome, or certain special situations

The minimum information required is:

- suspected Janssen medicinal product (doses, indication)
- date of therapy (start and end date, if available)
- batch or lot number, if available
- subject details (subject ID and country)
- gender
- age at AE onset
- reporter ID
- adverse event detail (AE verbatim in English), onset date, relatedness, causality, action taken, outcome, (if available)
- Janssen protocol ID

Product Quality Complaint (PQC)

A product quality compliant is defined as any suspicion of a product defect related to a potential quality issue during manufacturing, packaging, release testing, stability monitoring, dose preparation, storage or distribution of the product, or delivery system. Not all PQCs involve a subject. Lot and batch numbers are of high significance and need to be collected whenever available.

Examples of PQC include but not limited to:

- Functional Problem: e.g., altered delivery rate in a controlled release product
- Physical Defect: e.g. abnormal odor, broken or crushed tablets/capsules
- Potential Dosing Device Malfunction: e.g., autoinjector button not working, needle detaching from syringe

- Suspected Contamination
- Suspected Counterfeit

Serious Adverse Event (SAE)

See Serious Adverse Event Definition in Section 8.1 above

Hospitalization

See Hospitalization Definition in Section 8.1 above

Life-Threatening Conditions

Disease progression should not be recorded as an adverse event or serious adverse event term; instead, signs and symptoms of clinical sequelae resulting from disease progression/lack of efficacy will be reported if they fulfill the serious adverse event definition.

8.3.3.4 Unlisted (Unexpected) Adverse Event/Reference Safety Information

An adverse event is considered unlisted if the nature or severity is not consistent with the applicable product reference safety information. For a medicinal product(s) with a marketing authorization, the expectedness of an adverse event will be determined by whether or not it is listed in the applicable product information.

<http://www.darzalex.com/shared/product/darzalex/darzalex-prescribing-information.pdf>

For DARZALEX™ (daratumumab), the expectedness of an adverse event will be determined by whether or not it is listed in the Investigator's Brochure.

8.3.3.5 Special Reporting Situations

Safety events of interest for a Janssen medicinal product that require expediting reporting and/or safety evaluation include, but are not limited to:

- Drug exposure during pregnancy (maternal and paternal)
- Overdose of a Janssen medicinal product
- Exposure to a Janssen medicinal product from breastfeeding
- Suspected abuse/misuse of a Janssen medicinal product
- Inadvertent or accidental exposure to a Janssen medicinal product
- Any failure of expected pharmacological action (i.e., lack of effect) of a Janssen medicinal product
- Medication error involving a Janssen medicinal product (with or without patient exposure to the Janssen medicinal product, e.g., name confusion)
- Suspected transmission of any infectious agent via administration of a medicinal product
- Unexpected therapeutic or clinical benefit from use of a Janssen medicinal product
- Any failure of expected pharmacological action (i.e., lack of effect) of a Janssen medicinal product

These safety events may not meet the definition of an adverse event; however, from a Janssen Scientific Affairs, LLC perspective, they are treated in the same manner as adverse events. Special situations should be recorded on the Adverse Event page of the CRF.

Any special situation that meets the criteria of a serious adverse event should be recorded on a Serious Adverse Event Report Form and be reported to Janssen Scientific Affairs, LLC **within 24 hours of becoming aware of the event.**

8.3.3.6 Pregnancy

All initial reports of pregnancy must be reported to Janssen Scientific Affairs, LLC by the **PRINCIPAL INVESTIGATOR within 24 hours of becoming aware of the event** using the Serious Adverse Event Form. Abnormal pregnancy outcomes (e.g. spontaneous abortion, fetal death, stillbirth, congenital anomaly, ectopic pregnancy) are considered serious adverse events and must be reported using the Serious Adverse Event Form.

Any subject who becomes pregnant during the study must be promptly withdrawn from the study and discontinue further study treatment.

Because the effect of the Janssen medicinal product on sperm is unknown, pregnancies in partners of male subjects exposed to a Janssen medicinal product will be reported by the **PRINCIPAL INVESTIGATOR within 24 hours of their knowledge of the event** using the Serious Adverse Event Form. Depending on local legislation this may require prior consent of the partner.

Follow-up information regarding the outcome of the pregnancy and any postnatal sequelae in the infant will be required.

8.3.3.7 Maintenance of Safety Information

All safety data should be maintained in a clinical database in a retrievable format. The Mayo Clinic and PRINCIPAL INVESTIGATOR shall provide all adverse events, both serious and non-serious, in report format. However, in certain circumstances more frequent provision of safety data may be necessary, e.g. to fulfill a regulatory request, and as such the data shall be made available within a reasonable timeframe at Janssen Scientific Affairs, LLC request.

8.3.3.8 Procedures for Reporting Safety Data and Product Quality Complaints (PQCs) for Janssen Medicinal Products to Janssen Scientific Affairs, LLC

All adverse events and special situations whether serious or non-serious, related or not related, following exposure to a Janssen medicinal product are to be documented by the investigator and recorded in the CRF and in the subject's source records. Investigators must record in the CRF their opinion concerning the relationship of the adverse event to a Janssen medicinal product. All (serious and non-serious) adverse events reported for a Janssen medicinal product should be followed-up in accordance with clinical practice.

8.3.3.8.1 SAEs and Special Reporting Situations

All serious adverse events that have not resolved by the end of the study, or that have not resolved upon discontinuation of the subject's participation in the study, must be followed until any of the following occurs:

- The event resolves
- The event stabilizes
- The event returns to baseline, if a baseline value/status is available
- The event can be attributed to agents other than the study drug or to factors unrelated to study conduct
- It becomes unlikely that any additional information can be obtained (subject or health care practitioner refusal to provide additional information, lost to follow-up after demonstration of due diligence with follow-up efforts)

The Mayo Clinic and the PRINCIPAL INVESTIGATOR will transmit all SAEs, Adverse Events of Special Interest, and special situations following exposure to a Janssen product under study in a form provided by Janssen Scientific Affairs, LLC in accordance with Section 10, Transmission Methods, in English **within 24-hours of becoming aware of the event(s).**

In the event the study is blinded, the PRINCIPAL INVESTIGATOR will submit an unblinded SAE or pregnancy exposure report to Janssen Scientific Affairs, LLC.

All follow-up information for serious adverse events that are not resolved at the end of the study or by the time of patient withdrawal must be reported directly by the PRINCIPAL

INVESTIGATOR, **within 24 hours becoming aware**, to Janssen Scientific Affairs, LLC using the Janssen Scientific Affairs, LLC Serious Adverse Event Report.

All available clinical information relevant to the evaluation of a related SAE, Adverse Event of Special Interest, serious ADR or special situation is required.

- The Mayo Clinic and the PRINCIPAL INVESTIGATOR is responsible for ensuring that these cases are complete and if not are promptly followed-up. A safety report is not considered complete until all clinical details needed to interpret the case are received. Reporting of follow-up information should follow the same timeline as initial reports.
- Copies of any and all relevant extraordinary correspondences with regulatory authorities and ethics committees regarding any and all serious adverse events, irrespective of association with the Janssen Product under study, are to be provided to Janssen Scientific Affairs, LLC using a transmission method in Section 10 from this Exhibit within **24 hours of such report or correspondence being sent to applicable health authorities.**

